Bacillus Calmette-Guérin (BCG) was developed as a vaccine against tuberculosis, but many studies have shown its ability to induce potent protection against other infectious diseases: the so called non-specific effects (NSEs).[5] Moreover, BCG has non-specific clinical protective effects: early administration of BCG vaccination leads to reduced child mortality, mainly as a result of reduced neonatal sepsis, respiratory infections, and fever.[1, 5] NSEs of BCG are not limited to children, as a recent study in adolescents has shown a 70% decrease in the incidence of respiratory tract infections in individuals vaccinated with BCG compared to placebo.[6] In addition, a small Indonesian trial has shown that consecutive BCG vaccination for 3 months reduced the incidence of acute upper tract respiratory infections by 80% (95%CI=22-95%).[7] The non-specific beneficial effects of BCG are not restricted to infections, as BCG has also been used in patients with bladder cancer, to induce an improved reaction of the immune system, which prevents tumor progression and mortality.[8]

It has been recently demonstrated that the non-specific beneficial effects of BCG vaccination are due to epigenetic and metabolic reprogramming of innate immune cells such as myeloid cells and NK cells, leading to an increased antimicrobial activity, a process termed 'trained immunity'.¹² Upon stimulation with a pathogen, the innate immune system becomes primed and is able to react faster and more efficient to a secondary (and non-related) stimulus. In experimental studies, BCG has been shown to protect not only bacterial and fungal infections, but against viral infections such as influenza as well.[9] Furthermore, among humans receiving yellow fever vaccine virus, those who had received BCG had less viremia, and improved anti-viral responses compared to placebo treated subjects.[10] The observed effects are proposed to be due to modulation of the human innate immune system through 'trained immunity' and are long-lasting for at least one year

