2. RESEARCH QUESTIONS

Primary Objective:

1. To measure the efficacy of BCG vaccination among HRI and HCW in preventing infection with SARS-CoV2 in the United States.

[figure not shown]
Secondary Objective:

1. To measure the efficacy of BCG vaccination among HRI and HCW in mitigating the severity of Covid-19 disease in the United States.

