4. INVESTIGATIONAL PRODUCT

a. Name and description of investigational product(s)

Participants that are randomized in the active arm will receive BCG vaccine, the FDA-approved TICE® BCG (for intravesical use) BCG LIVE strain in the United States.

b. Summary of findings from non-clinical studies

BCG has been shown to have the ability to train the innate immune system in an in vitro and in vivo setting. eg. when human monocytes are incubated for 24h in vitro with BCG and after a week are re-challenged with another (part of a) pathogen, the cytokine production is increased, compared to non-BCG trained monocytes.[13] BCG also protects in experimental models of viral infections (e.g. influenza) in murine models.¹³

c. Summary of findings from clinical studies

BCG vaccine has been shown to induce training of the innate immune system in vivo, just as heterologous effects of the adaptive immune system (e.g. increased cytokine production by monocytes and lymphocytes of BCG-vaccinated individuals), which is thought to have a protective effect in countries with a high infectious pressure (e.g. most third world countries).^{17,18} After vaccination with BCG, immune cells isolated from healthy individuals react with an increased production of proinflammatory cytokines after stimulation with both specific (MTB) and non-specific (bacterial, viral, fungal) stimuli. Adolescents vaccinated with BCG have shown a 70% decrease in the incidence of respiratory tract infections compared to placebo⁹. In a small Indonesian trial, consecutive BCG vaccination for 3 months reduced the incidence of acute upper tract respiratory infections by 80% (95%CI=22-95%).[7]

d. Summary of known and potential risks and benefits

The potential benefit for subjects randomized to the BCG-arm is that administration of the vaccine could prevent SARS-CoV-2 infection and lower risk on developing severe illness caused by SARS-CoV-2.

Potential risks include only the well-known side effects of both the vaccines. A short summary of the most common side effects includes: discomfort at the injection site, scarring at injection site, fevers, nausea, vomiting. Severe but very uncommon side effects are: neurological symptoms such as injection site abscesses, BCG lymphadenitis, disseminated BCG diseases, osteitis, osteomyelitis, anaphylaxis, formation of keloid/lupoid, suppurative lymphadenitis. A complete list of known side effects can be found in the information product insert.

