6. STUDY PARAMETERS/ENDPOINTS

a. Primary study endpoint

Incidence of rt-PCR-confirmed SARS-CoV2 infection following BCG vaccination compared to that following placebo.

b. Secondary study endpoint

In individuals who test positive for Covid-19, the proportion with severe disease following BCG vaccination compared to placebo, as defined by the following necessary care levels: non-hospital care; patient hospitalized but no oxygen required; hospitalized and oxygen required; patient treated in intensive care and/or on mechanical ventilation; patient died.

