Participants will complete intermittent surveys via an electronic system every 7 days to assess the presence of any flu-like symptom, including sore throat, fever, headache, malaise, and cough. Note that this is part of routine surveillance for Covid-19 in health workers at the United States site. Consent forms will ask for consent to access this survey information.

Any positive response on the survey will trigger a nasopharyngeal, oral and/ or rectal swab to be collected to test for Covid-19 via rt-PCR

All participants, regardless of survey responses, will have serology for Covid-19 tested at 4 week intervals during the follow-up period (6 months)

If a participant completes the follow-up period and does not test positive for disease, their study participation is complete

If a participant does test positive for disease, their disease status will be ascertained for up to two months or until an outcome is available through one of the following mechanisms: (1) an electronic survey if they are not admitted to the hospital, including questions about the number of days they are ill, daily fever, and other symptoms; or (2) if they are admitted to the hospital, ordinal outcomes for disease severity will be extracted from the hospital's electronic medical records system.

During the first week of follow-up, all participants will actively be asked about any adverse events; thereafter, participants will report unsolicited AEs through the electronic survey. Vaccine related adverse events will be graded using the FDA guidance (<https://www.fda.gov/media/73679/download>) and noted using WHO-recommended Adverse event following Immunization forms (AEFI; <https://vaccine-safety-training.org/classification-of-aefis.html>).

Participants will have the option of donating 12 mL of blood for plasma (serology) and PBMCs for secondary analysis of immune correlates and for future analysis based on covid19-specific IgM and IgG. If they do not donate 12mL of blood, a fingerstick will be required for baseline COVID19 serology.

Dried Blood Spot (DBS): all participants will self-collect DBS samples at week 4, 8, 12, 16, 20 and 24. Envelopes to store the DBS are provided upon enrollment and can be mailed or dropped off at work and picked up by study coordinators.

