c. Primary study parameter(s)

The primary endpoint, development of COVID19 infection, we will use the Cox proportional-hazards model to calculate hazard ratios for the development of Covid-19. This will be reported as the proportion of individuals receiving the intervention who are PCR-positive or seroconvert.

d. Secondary study parameter(s)

Disease severity as discussed above and based on guidelines proposed by the World Health Organization. We will use the Chi square for significance to calculate the risk ratios for the development of severe Covid-19 disease. Disease severity will be based on the level of care required for individuals who test positive for COVID19 as follows: non-hospital-based care; patient hospitalized but no oxygen required; hospitalized and oxygen required; patient treated in intensive care and/or on mechanical ventilation; patient died. Additional WHO criteria for severity include severe pneumonia, respiratory failure, acute respiratory distress syndrome, sepsis and septic shock. Days absent will also be self-reported via the RedCap Research App. Immunology and epigenetic studies for innate training be implemented, but in brief, immune cells will be stimulated with non-specific (LPS, mitogen, BCG) and COVID19-specific antigens with immune function measured by ELISA and flow cytometry. Epigenetic studies are discussed in more detail below.

e. Other study parameters

Continuous baseline characteristics will be reported as mean and standard deviation or median and inter-quartile range, as appropriate. Categorical baseline characteristics will be reported as count and percentage. No statistical testing for baseline characteristics will be performed.

f. Synthesis

In this trial, the BCG vaccine will be used in hospital personnel during the epidemics to prevent infection with the new SARS-CoV-2 virus. The risk of the BCG vaccine is very well known (see product inserts) and only minor local side effects (redness, local pain) are common. The benefits of BCG vaccination based on earlier clinical studies are expected to be a reduction in infection and morbidity of at least 25% compared to unvaccinated individuals, and potentially much higher. These effects are mediated by the capacity of BCG to induce trained immunity and may represent an important tool for protection against SARS-CoV-2 virus infection until a specific effective vaccine is developed.

g. Epigenetic and Immune Corollary Studies

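### If section 6.a governs, symptom-triggered PCR lets the primary endpoint differ between arms with no infection prevented; section 10.c removes most of this but conflicts with 6.a

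*Combined protocol and SAP*

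**What the plan says.** The primary objective in section 2 is to prevent infection. Section 6.a sets the endpoint: "Incidence of rt-PCR-confirmed SARS-CoV2 infection following BCG vaccination compared to that following placebo". Section 7.c surveys participants every 7 days "to assess the presence of any flu-like symptom, including sore throat, fever, headache, malaise, and cough", and then states: "Any positive response on the survey will trigger a nasopharyngeal, oral and/ or rectal swab to be collected to test for Covid-19 via rt-PCR". Sections 3.a and 7.a also make PCR in follow-up conditional on symptoms. No PCR is scheduled for everyone during follow-up. Stool swabs from symptom-free participants are optional, are tested later, and serve secondary objectives.

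Several passages imply that treatment may change the trigger:
- Section 1 cites a "70% decrease in the incidence of respiratory tract infections in individuals vaccinated with BCG compared to placebo"; section 11.e gives a range of 30 to 70% for earlier studies.
- Section 1 hypothesises an effect on susceptibility, on severity, or on both, and the secondary objective is: "To measure the efficacy of BCG vaccination among HRI and HCW in mitigating the severity of Covid-19 disease in the United States".
- Section 4 (Investigational Product), part d, lists as common side effects "discomfort at the injection site, scarring at injection site, fevers, nausea, vomiting".

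Other passages provide a safeguard. Section 7.c has serology every 4 weeks for all participants, whatever they answer on the survey. Section 10.c reports the primary endpoint as the "proportion of individuals receiving the intervention who are PCR-positive or seroconvert". Section 10.g uses baseline serology to remove people with earlier infection from the analysis. Nothing reconciles 6.a with 10.c, and no comparison of testing between arms is described.

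**The concern.** Under 6.a an infection counts only if it is swabbed, and it is swabbed only if the participant reports a symptom. An infected person can be missed in two ways that may depend on treatment. A symptom-free infection is found only if an unrelated symptom happens to prompt a swab, and BCG may make unrelated respiratory symptoms rarer. An infection that BCG makes milder may produce no report at all. Both would lower the PCR-confirmed rate on BCG with the same number of infections in each arm. Fever after injection would prompt extra swabs on BCG and so raise it.

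At stake is the meaning of the main result. A lower PCR-confirmed rate would be a valid finding about symptomatic COVID-19, but the stated objective is prevention of infection. Section 10.b would also stop the trial early on an interim p-value, so the endpoint behind that p-value matters.

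**Working it through.** **The plan's own figure.** Section 10.a: 5% symptomatic COVID-19, relative risk 0.4, two-sided 0.05, 80% power. With 5% v 2%, n per arm = [1.96·√(2·0.035·0.965) + 0.842·√(0.05·0.95 + 0.02·0.98)]² / 0.03² = 588, or 653 with continuity correction. The planned 700 per arm exceeds both and gives 86% power (expected cases 35 v 14). The mismatch is conservative and does not affect this point.

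**Detection model, no effect on infection.** Let S be the share of infections with symptoms, w the weekly probability of reporting an unrelated symptom, and 3 the number of weekly surveys in the detectable window.

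Detection D = S + (1 − S)·q, with q = 1 − (1 − w)³. The apparent risk ratio (RR) is D on BCG divided by D on placebo.

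Assumptions, not plan figures: S = 0.6, w = 0.10 on placebo, independent weekly reports, every symptomatic infection detected, no PCR from other sources. The 3 weeks follow the roughly 21 days that section 7.c gives for RNA in stool; swabs from other sites may differ.

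- Placebo: q = 1 − 0.9³ = 0.271; D = 0.6 + 0.4·0.271 = 0.708.
- BCG, 70% fewer unrelated symptoms (w = 0.03): q = 0.087; D = 0.635; RR = 0.90.
- BCG, 30% fewer (w = 0.07): q = 0.196; D = 0.678; RR = 0.96.
- At 70%, varying S and w: S = 0.8, w = 0.05 gives RR 0.98; S = 0.4, w = 0.15 gives RR 0.76.
- With a 1-week window (q = w): 0.612/0.640 = 0.96 at 70%, and 0.628/0.640 = 0.98 at 30%.

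**Milder infection added.** Suppose BCG halves S from 0.6 to 0.3 (assumed).
- Unrelated symptoms at 10% in both arms: (0.3 + 0.7·0.271)/0.708 = 0.490/0.708 = 0.69.
- Also 70% fewer unrelated symptoms on BCG: (0.3 + 0.7·0.087)/0.708 = 0.361/0.708 = 0.51.
- No unrelated symptoms in either arm: 0.3/0.6 = 0.50.

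**Effect on the test.** With 700 per arm, 5% PCR-confirmed on placebo and 5%·RR on BCG, the chance of a significant result favouring BCG is 6% at RR 0.9, 29% at 0.7 and 69% at 0.5. It should be 2.5%.

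**Adding seroconversion as in section 10.c.** If serology finds a share v of the infections that PCR misses, detection becomes D + (1 − D)·v. For example, at v = 0.9 the first scenario gives 0.963/0.971 = 0.99.

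| Scenario | PCR only | v = 0.5 | v = 0.7 | v = 0.9 |
|---|---|---|---|---|
| Unrelated symptoms 70% lower, S = 0.6 | 0.90 | 0.96 | 0.98 | 0.99 |
| S from 0.6 to 0.3, no unrelated symptoms | 0.50 | 0.81 | 0.90 | 0.97 |

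At v = 1 both ratios are 1.00. Extra swabs from post-injection fever are not modelled, because the documents give no rate; they would move the ratio upward.

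**The case against.** The strongest reply is that the plan already contains the remedy. Section 10.c counts seroconversion, section 7.c collects serology from everyone regardless of symptoms, and section 10.g removes people positive at baseline. If 10.c governs, the bias is small with good serology. This stands, and it makes the point conditional on 6.a. It does not dispose of it. The two definitions differ, the samples are self-collected and returned by mail or drop-off, and section 10.g describes the assay as still in development. At v = 0.5 to 0.7 a residual bias remains.

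The size is also open to challenge, fairly. The 70% is the top of the plan's own 30 to 70% range and concerns respiratory infections, whereas headache and malaise need not be infectious. At 30%, or with a 1-week window, the testing effect alone is slight.

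A reader might infer that the trial would show 50% false efficacy. The documents do not support that. The ratio of 0.50 follows directly from the assumed halving of the symptomatic share, and section 6.b measures severity by level of care, not by a shift to symptom-free infection. A reader might also infer that testing will differ between arms in BCG's favour. The plan's premises make a difference possible, but post-injection fever pulls the other way and no testing data are given.

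**Conclusion.** The point holds conditionally. If 6.a governs, PCR-confirmed infection can differ between arms without any infection being prevented, so a PCR-only result cannot by itself carry a claim about infection. Under the stated assumptions, fewer unrelated symptoms alone give an apparent RR of about 0.90 (70% reduction) to 0.96 (30%). A halved symptomatic share, which is purely an assumption, would bring it to about 0.5 to 0.7. Milder infection is therefore the larger threat and fewer unrelated symptoms a modest one. The net direction is uncertain.

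It would be too strong to say that the plan cannot tell fewer infections from milder ones. The 4-weekly serology can do so if it is sensitive and complete and if it is part of the governing endpoint. The remaining defect is that 6.a leaves it out while 10.c includes it.

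**What to change.** 1. Reconcile 6.a to 10.c. Define the primary infection endpoint, for both arms, as a positive PCR or seroconversion on scheduled serology among participants seronegative at baseline.
2. Report symptom-triggered PCR cases separately as symptomatic COVID-19, the outcome on which section 10.a bases its sample size.
3. Tabulate swabs per participant and percent positive by arm, with completeness of the serology samples by arm.
4. State how seroconversions enter the Cox analysis: an interval-censored model, or a fixed dating rule applied to both arms. Correct the serology schedule as well. Section 1 and the follow-up data table say every two weeks, whereas sections 3.a, 7.c and 10.a give 4-week intervals.
5. State a confirmatory reading rule for seroconversion, or a sensitivity analysis for false positives.

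The cost is endpoint and analysis wording plus one table; no new samples are needed. There are two downsides. Seroconversions are dated only to a 4-week interval. Imperfect specificity also accumulates over six follow-up tests: with independent errors and an assumed per-test specificity of 99.9% or 99%, false seroconversions reach 1 − 0.999⁶ = 0.6% or 1 − 0.99⁶ = 5.9%. The upper figure rivals the 5% expected event rate and would dilute a true effect, which is why item 5 is needed.

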Unblinded personnel will not be involved in the collection and analysis of study data other than the baseline eligibility criteria.

The end of the study is defined as the last patient's last entry in the electronic data capture system.

Informed Consent and Eligibility

The following types of procedures will be conducted as indicated below:

Medical history will be obtained from patient medical record/clinical chart. Informed Consent will be obtained to access these records. When information cannot be obtained or is not available from the patient medical record/clinical chart, it will be obtained via patient interview.

Visual examination will be conducted solely to look for existing BCG vaccination scars.

Symptom evaluation will be conducted via an electronic survey administered to participants every 7 days.

Height, weight, HIV status **and pregnancy** status will be collected as self-reported information. If unknown, a urine pregnancy test will be performed.

Nasopharyngeal, oral and/ or rectal **swabs** will be collected for rt-PCR test for SARS-CoV2 infection if a participant develops symptoms consistent with Covid-19.

If a participant does not know their PPD/IGRA status from within the last 24 months (all health care providers should have this information), an IGRA can be performed to evaluate eligibility.

Study participants have the option of donating blood via phlebotomy (for serological test for Covid-19 disease and PBMCs for immune correlates) or providing a fingerstick and dried blood spot (for serologic test for Covid-19).

Data will be collected at four time points/periods: (1) after consent, (2) at baseline, (3) during follow-up period, and (4) at study end.

Data to be collected during screening includes medical history, visual exam results, results of rt-PCR and serological test results.

Data to be collected during baseline enrollment includes eligibility confirmation, demographic information, risk factors, randomization assignment, confirmation of BCG vaccination/placebo, any immediate reactions to BCG vaccination/placebo. Subjects may also be asked to share a picture of just the injection site. Sharing the picture of the injection site is optional and will not be available to blinded staff members until the end of the study.

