Structural imaging by MRI allows sensitive assessment of most cognitive disorders, a partial list of which includes: dementia, Alzheimer's, Parkinson's, mild cognitive impairment, vascular cognitive impairment, and cerebrovascular disease. When combined with longitudinal imaging, MRI becomes even more sensitive and can establish cognitive status trajectory well before these neuropathologies are clinically obvious[24-26]. Whole brain high-resolution MRI with coronal slices will be used to image the entire brain, hippocampus and temporal lobe to assess the extent of regional atrophy, including volume loss, and cerebrovascular disease using both visual rating scales and automated segmentation methods to measure cognitive changes. Measures will include assessment of vascular dementia, postero-medial parietal lobe atrophy, posterior cingulate gyrus, hippocampal-mediated temporal lobe, atrophy in inferior frontal lobe, visual cortex, insula, hypothalamus, midbrain, caudate, putamen, anterior hippocampi, macrohaemorrhage, fronto-temporal degeneration, atrophy of medial temporal structures and whole-brain atrophy. This strategy will provide a sensitive measure of cognitive status at each time point and trajectory that will ensure we obtain rapid insight into the effects of COVID-19 and BCG vaccination on cognition.

9. SAFETY REPORTING**a. Temporary halt for reasons of subject safety**

The investigators will suspend the study if there is sufficient ground that continuation of the study will jeopardize subject health or safety. The investigator will notify the IRB without undue delay of a temporary halt including the reason for such an action. The study will be suspended pending a further positive decision by the IRB. The investigator ensure that all subjects are kept informed.

b. AEs, SAEs and SUSARs**i. Adverse events (AEs)**

Adverse events are defined as any undesirable experience occurring to a subject during the study, whether or not considered related to the investigational product, the placebo or the trial procedures. Adverse events can be self-reported by the subjects using the mobile application. All adverse events reported spontaneously by the subject or observed by the investigator or his staff will be recorded and assessed per institutional IRB and policies.

ii. Expected mild Adverse events

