Although BCG vaccination almost always causes local reactions, serious or long-term complications are rare. Almost all recipients of BCG will experience vaccine site erythema and development of a small pustule. Slight tenderness at the puncture site may be encountered as well as some itching. The initial skin lesions usually appear within 10–14 days and consist of small red papules at the site. The papules reach maximum diameter (about 3 mm) after 3 to 4 weeks, after which they may scale and then slowly subside.

Theoretically it is feasible that a HCW BCG vaccinated could shed attenuated live BCG and transmit this to an immunocompromised patient. While theoretically feasible, we found no case reports of such events. Further, the ability to keep the vaccine site covered is an exclusion criterion. Study participants will be notified of the expected pustule formation and the need to keep it covered by gauze and clothes during the period it is draining. Before the pustule drains, it has characteristic fluctuant appearance and should be covered with gauze from the time fluctuance develops.

iii. Expected rare, serious Adverse events:

Approximately 1 in 1000 to 1 in 10,000 will experience suppurative lymphadenopathy including moderate axillary or cervical lymphadenopathy and induration and subsequent large pustule formation. While local usually resolved within 3-4 weeks, supportive lymphadenopathy can persist for as long as 3-6 months after vaccination. There is not definitive management for suppurative lymphadenitis and treatment will be managed on a case by case basis with some undergoing “watchful surveillance and others drained with incision and drainage. All adverse events will be discussed by the site and overall PIs.

More serious local reactions include ulceration at the vaccination site, regional suppurative lymphadenitis with draining sinuses, and caseous lesions or purulent draining at the puncture site. These manifestations might occur up to 5 months after vaccination and could persist for several weeks. The intensity and duration of the local reaction depends on the depth of penetration of the multiple puncture device and individual variations in patients' tissue reactions.

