10. SAMPLE SIZE AND STATISTICAL ANALYSIS

Data will be reported quantitatively. All analyses will be performed from the intention-to-treat principle. Missing data will be dealt with by multiple imputation using the mice package in R.

a. Sample size calculation

The study in the United States will include at least three sites: Houston (BCM and MD Anderson Cancer Center considered as 'one site' due to proximity), Texas A&M University (TAMU), and Cedars Sinai Medical Center (CSMC). TAMU will enroll 1400 individuals. The proposed enrollment sample size is designed to provide 80% power to detect a 60% vaccine efficacy (a relative risk of 0.4 among the vaccinated). This is based on the observed three-fold decline in respiratory infections in the South Africa adolescent cohort with 80% power and 0.05 type 1 error in a two-tailed test. We expect 5% of study participants to develop symptomatic COVID19 during follow-up, therefore a sample size of 1400, with 700 receiving intervention and 700 receiving placebo. We do not expect significant loss to follow up among HCWs (there has been zero LTF after the first 500 participants). We will plot Kaplan-Meier curves comparing COVID19 disease between the BCG and placebo groups and report hazard ratios and p-values using Cox proportional hazard models. DBS samples will be collected at baseline and weeks 4, 8, 12, 16, 20 and 24 post intervention. PBMCs and plasma donations are optional at baseline, 12 and 24 weeks. If interim analysis identifies a large proportion of participants to be seropositive before intervention, power analysis will be evaluated and an amendment will be submitted if additional participants need to be recruited.

b. Interim analysis

One month after the first 100 participants are enrolled, an interim analysis will be held by the independent statistician of the trial. Data will be exported independently from all sites and then data collated and merged for the interim analysis). The above described statistical analysis will be evaluated as well as safety profile. Enrollment is expected to occur within the first two months of launch. Interim analysis will occur based on study enrollment and three to six interim analysis will occur based on temporal dynamics of enrollment as requested by the DSMB. We will stop the clinical trial early if the p-value of any interim analysis is smaller than the pre-specified type-1 error cutoff. Each interim analyses will be reported to the DSMB.

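### Common severity grading is reserved for adverse events judged vaccine related; that judgement has no stated assessor, timing or criteria, so a comparison of graded harms is open to attribution bias

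*Combined protocol and SAP*

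**What the plan says.** Section 7.c (follow-up procedures) states that "Vaccine related adverse events will be graded using the FDA guidance" and that these events are "noted using WHO-recommended Adverse event following Immunization forms". No other severity scale for adverse events is named in the protocol.

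Section 9.b.i defines an adverse event broadly, "whether or not considered related to the investigational product, the placebo or the trial procedures", and says that reported or observed events "will be recorded and assessed per institutional IRB and policies".

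On what could reveal the arm, section 9.b.ii says: "Almost all recipients of BCG will experience vaccine site erythema and development of a small pustule". It puts the usual onset of lesions at 10 to 14 days and says participants are told to expect the pustule. Section 5.e describes the placebo as 0.1 mL of saline, matched on volume and colour.

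On blinding, section 7.a says: "Unblinded personnel will not be involved in the collection and analysis of study data other than the baseline eligibility criteria". It also withholds injection-site photographs from blinded staff until the study ends.

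On use of the data, section 10.b says of the interim analysis: "The above described statistical analysis will be evaluated as well as safety profile". Section 9.c has the DSMB review adverse events monthly, with an unblinded statistician.

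**The concern.** Read together, 7.c and 9.b.i make attribution the gate to common grading. An event called vaccine related gets the FDA grade and the AEFI form. An event called unrelated is recorded, but the plan promises it no common grade.

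That gate may not treat the arms alike. Because unblinded staff stay out of follow-up data collection, nominally blinded staff receive the adverse event reports. A local reaction is itself an adverse event, reported through the same electronic route as a fever or a bout of nausea. Section 4.d of the investigational product chapter lists fever, nausea and vomiting among the common BCG side effects, and these symptoms are non-specific. A reviewer who also holds a report of a pustule from the same participant may call the symptom vaccine related more readily than for a participant without one.

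At stake is any table of graded events shown to the DSMB or in the final report. It could show an excess on BCG that comes from attribution. Separately, and even with perfect blinding, a true but unexpected BCG effect judged unrelated would carry no common severity grade.

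**Working it through.** The plan states no figure on this point, so there is nothing to reproduce. The check is a comparison of sections, followed by an illustration with assumed rates.

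**1. Is grading conditional on relatedness?** Yes as written in 7.c. Section 9.b.i does not extend the FDA scale to other events.

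**2. Who judges relatedness, when, and masked to what?** Not stated. Section 9.b.iii says only that the site and overall principal investigators will discuss adverse events. It does not assign the relatedness decision or give criteria.

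**3. Which events could be affected?** Section 7.c actively solicits events in the first week, days 0 to 7. Lesions usually appear on days 10 to 14 (9.b.ii). First-week events can therefore be judged before the lesion, although the plan does not require it. Later events are unsolicited and can fall after the lesion. Follow-up runs to at most 168 days (3.a), so the solicited week covers 7 of up to 168 days.

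**4. Illustration of size.** The 700 per arm comes from 10.a. The true adverse event risk (equal in both arms) and the attribution probabilities are assumptions.

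Graded events in an arm = 700 × true risk × probability of being judged vaccine related.

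At 10% true risk each arm has 700 × 0.10 = 70 events:

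| Attribution, BCG v placebo | Graded, BCG | Graded, placebo | Apparent risk ratio |
|---|---|---|---|
| 50% v 50% | 70 × 0.50 = 35 | 70 × 0.50 = 35 | 1.00 |
| 50% v 40% | 35 | 70 × 0.40 = 28 | 1.25 |
| 50% v 25% | 35 | 70 × 0.25 = 17.5 | 2.00 |

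The ratio depends only on the two attribution probabilities. The counts scale with the true risk: at 5% they are 17.5 v 14 and 17.5 v 8.75; at 30% they are 105 v 84 and 105 v 52.5.

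**5. Allowing for events judged before the lesion.** Suppose half of the events are attributed at 50% in both arms and only the other half differ. Placebo attribution becomes 0.5 × 0.50 + 0.5 × 0.40 = 0.45, or 0.5 × 0.50 + 0.5 × 0.25 = 0.375. Graded placebo events are 70 × 0.45 = 31.5 or 70 × 0.375 = 26.25, and the ratios fall to 35/31.5 = 1.11 or 35/26.25 = 1.33.

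**6. If every event is graded.** The expected comparison is 70 v 70, ratio 1.00, whatever the attribution.

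**The case against.** The case against has real force, and most of it limits the point.

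- **Timing.** A reader might infer that relatedness is judged only once the lesion has shown the arm. The documents do not say this. They give no timing, and the solicited week comes before the usual onset.
- **Exposure of the assessor.** Investigators are formally blinded, photographs are withheld from blinded staff, and follow-up is by electronic survey. Differential attribution is a risk, not a documented fact. The photograph rule does not, however, cover written reports of a local reaction.
- **Data free of attribution.** The survey every 7 days (7.c) covers fever, headache and malaise in everyone, and 9.b.iii mentions symptom diaries with results reviewed by the DSMB every 4 weeks. All adverse events are recorded. Serious events go to the DSMB regardless of attribution (9.b.v), and the board may ask for more data (9.c). Only the common grade and the form are at issue, mainly for non-serious events.
- **Pooling.** A reader might infer that the sites use different scales that cannot be combined. No site scale is named, and section 4.d on site coordination gives all sites the same REDCap form and data dictionaries. What stands is that no common grade is promised for these events.
- **No test to distort.** Section 10 specifies no between-arm test of graded events, and no halting rule in 9.d uses the FDA grade. The counts above could be turned into a false-alarm rate, but that would describe an analysis the plan does not contain, with attribution rates it does not give.
- **Meaning of the phrase.** The AEFI label is temporal, so the wording in 7.c might be meant to cover all post-injection events in both arms. If so, the sentence should say so; as written, the causal reading is the natural one.

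**Conclusion.** The concern holds in limited form and is minor. The plan makes the common grade and the AEFI form depend on a relatedness judgement that it does not define. For events after about day 10, a reported BCG site reaction may inform that judgement. A between-arm table of graded events is therefore at risk of attribution bias, and unexpected effects judged unrelated would lack a common grade.

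The documents do not show that bias will occur, and its size cannot be derived from them. The illustrative ratios of 1.25 and 2.00, or 1.11 and 1.33 if half of the events are unaffected, rest wholly on assumed attribution rates and on equal true risk in the arms.

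**What to change.** - In 7.c, state that every adverse event in both arms and at all sites, whatever its judged cause, will be graded on the FDA scale.
- Record relatedness as a separate eCRF field that does not decide whether an event is graded.
- State that between-arm harm tables (interim, DSMB and final) use all graded events, with vaccine-related events as a supportive listing.
- Align 9.b.i with this text.

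The cost is protocol wording, one eCRF field and slightly more grading work. The events are already recorded under 9.b.i, so no extra visits or participants are needed.
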